2.1 Primary Objectives

Evaluate the efficacy of single agent camidanlumab tesirine in patients with relapsed or refractory Hodgkin lymphoma (HL).

2.2 Secondary Objectives

- Characterize additional efficacy endpoints of camidanlumab tesirine
- Characterize the safety profile of camidanlumab tesirine
- Characterize the pharmacokinetic (PK) profile of camidanlumab tesirine
- Evaluate the immunogenicity of camidanlumab tesirine
- Evaluate the impact of camidanlumab tesirine treatment on health-related quality of life (HRQoL)

2.3 Exploratory Objectives

- Assess the pharmacodynamic effects of camidanlumab tesirine
- Characterize tumor and tumor-associated nontumor cells (TANT), as well as immunological relevant parameters, in baseline tumor tissue
- Evaluate genetic alterations characterizing HL and their evolution upon camidanlumab tesirine treatment
- Explore exposure-response relationships affecting safety and efficacy of camidanlumab tesirine
- Explore correlations between clinical activity or safety of camidanlumab tesirine and tumor and/or blood biomarkers

3 Study Design

This is a Phase 2, multi-center, open-label, single-arm study. The study will enroll approximately 100 patients.

Because of the considerable overall response rate (ORR) observed in the ADCT-301-001 Phase 1 trial in HL patients and the anticipated recruitment projections, an formal interim analysis for futility is not warranted.

3.1 Sample Size Consideration

The primary hypothesis is that the overall response rate based on central review for patients treated with camidanlumab tesirine is significantly greater than 35% (i.e., $H_0: p \leq 0.35$ vs. $H_a: p > 0.35$). This hypothesis will be tested at a type I error of 0.05 (2-sided).

Using nQuery exact test for single proportion, a sample size of 100 patients has >98% power to distinguish between an active therapy with a 55% true response rate from a therapy with a response rate of 35% or less with a 1-sided alpha of 0.025. This sample size will provide adequate precision for the point estimate of ORR in the expected range and a robust population for safety evaluation.

3.2 Randomization

This study is not randomized.

3.3 Modifications to the statistical section of the protocol

NA.

4 Statistical methods

All analyses use SAS® version 9.4 or higher. All available data will be used in the analyses, and important data will be included in data listings, sorted by patient, and by visit within patient. Missing data will not be imputed, except via censoring in survival analyses and as otherwise specified.

Unless otherwise noted, categorical data will be presented using counts and percentages, with the number of patients in the analysis population as the denominator for percentages. Percentages will be rounded to one decimal place, except 100% will be displayed without any decimal places and percentages will not be displayed for zero counts. Continuous data, unless otherwise noted, will be summarized using the number of observations (n), mean, standard deviation (std), median, minimum, and maximum. Minima and maxima will be rounded to the precision of the original value, and means, medians, and 95% confidence intervals (CIs) if presented will be rounded to 1 decimal place greater than the precision of the original value. The std will be rounded to 2 decimal places greater than the precision of the original value, up to a maximum of 3 decimal places.

4.1 Analysis Populations

4.1.1 All-Treated Population

All patients who receive at least 1 dose of camidanlumab tesirine. This population will be used in the primary analyses of efficacy and safety.

4.1.2 Per-Protocol Population

All patients in the all-treated population who met the inclusion/exclusion criteria, did not take a prohibited concomitant treatment, nor had other protocol deviation which have important impact on efficacy results.

4.1.3 Stem Cell Transplant (SCT) Population

All patients who have responded to camidanlumab tesirine and undergo hematopoietic stem cell transplant (HSCT) (either autologous or allogeneic) after permanent discontinuation of camidanlumab tesirine treatment (without any intervening anticancer therapy to treat relapsing disease but mobilization/conditioning treatment for HSCT is allowed).

4.1.4 CAR-T Population

All patients who have received Chimeric Antigen Receptor T-cell (CAR-T) therapy as the immediate subsequent anticancer therapy (mobilization/conditioning treatment for CAR-T is allowed).

4.1.5 Patient Reported Outcome (PRO) Population

All patients in the all-treated patients with baseline score (at least one instrument) and at least 1 postbaseline score (in at least one instrument).

4.2 Patient Disposition

The number and percentage of patients enrolled and treated in the study will be presented along with the number and percentage of patients in each analysis population. In addition, the number and percentage of patients who withdrew from study treatment and who discontinued the study for each reason will be tabulated.

Patient disposition data will be listed.

4.3 Protocol Deviations

The number and percentage of patients with any important clinical study report (CSR) reportable protocol deviation will be summarized overall and by type of deviation. The pre-defined important CSR reportable protocol deviations are listed below; in addition, any other protocol deviations deemed by ADCT medical to be important CSR reportable deviations will be included in the summary.

1. Patients entered the study even though they did not satisfy the entry criteria
2. Patients received a prohibited concomitant treatment during the study
3. Patients who met criteria for mandatory withdrawal of study drug during the study but did not have study drug withdrawn
4. Patients who received the wrong treatment or incorrect dose, specifically:
 - Actual dose of study drug was greater than 15% more or less than protocol defined planned dose level.
 - Patients started next cycle less than 18 days after Day 1 of the most recent treatment cycle.

Important protocol deviations will be listed.

4.4 Demographic and Baseline Characteristics

Demographic and baseline characteristics will be tabulated for the all-treated population. Variables include the following:

- Sex (female, male)
- Race (white, black or African American, Asian, American Indian or Alaska native, native Hawaiian or other Pacific Islander, other)
- Ethnicity (Hispanic or Latino, not Hispanic or Latino)
- Age (years)
- Age group (<55, ≥ 55 - < 65, ≥ 65 - < 75, ≥ 75 years), (12-17 years, 18-64 years, 65-84 years, ≥ 85 years)
- Height (cm)
- Weight (kg)
- Body mass index (BMI) (kg/m^2)

- Eastern Cooperative Oncology Group (ECOG) performance status

Demographic and baseline characteristics data will be listed.

4.5 Cancer History and Medications History

Cancer history will be presented for the all-treated population. Cancer history will include the following variables:

- Duration since diagnosis
- Classical Hodgkin lymphoma subtype (nodular sclerosis classical Hodgkin lymphoma [cHL], lymphocyte-rich cHL, mixed cellularity cHL, lymphocyte-depleted cHL, and other)
- Stage of disease at study entry (Stage I, II, III, IV; constitutional symptoms A, B; Subtype E, X, S)
- Cytogenetic analysis
- Immunophenotypic analysis (results available yes; CD15, CD30, PAX5, CD3, CD20, CD45, CD79a, BCL6, etc.)

Prior anticancer procedure or therapy will include the following variables:

- Number of lines of therapy/regimens per patient
- Response to the first line and/or most recent line of prior systematic therapy
- Any prior radiotherapy for the current malignancy (yes, no)
- Any prior surgery for the current malignancy (yes, no)
- Reason for stopping therapy (progression, lack of response, toxicity, completed treatment, partial or complete remission, other)
- Best response (complete response [CR], partial response [PR], stable disease [SD], progressive disease [PD], not evaluable [NE])
- Any prior stem cell transplant (yes, no)
- Primary reason for transplant ineligibility prior to entering the study
- Type of transplant (allogenic, autologous, both, other)

Medical and cancer history data will be listed. Results of cytogenetic analysis and immunophenotypic analysis will be listed. Tumor tissue biopsy collection will not be listed, but will be contained in datasets.

Prior anticancer surgery, radiotherapy, systemic therapy, and stem cell transplant data will be listed.

4.6 Prior or Concomitant Medications (other than anticancer therapies)

All medications taken from the ICF signature date or within 14 days prior to Cycle 1 Day 1 (C1D1), whichever is earlier, and until at least 30 days after last dose of study drug are to be reported in the CRF pages.

All medications will be coded using the World Health Organization-Drug Dictionary (WHO-DD).

- Prior medications are those the patient used prior to the first dose. Prior medications can be discontinued before the first dose or can be ongoing during the treatment phase.
- Concomitant medications are any treatments received by the patient concomitantly to any camidanlumab tesirine from the first dose to the last dose + 30 days. A given medication can be classified both as a prior medication and as a concomitant medication. Concomitant medications do not include medications started 30 days after the last dose.

Any technical details related to computation, dates, and imputation for missing dates are described in Section 7.

Prior medications will be listed together with concomitant medications.

4.7 Exposure to Treatment

4.7.1 Extent of Camidanlumab Tesirine Exposure

Camidanlumab tesirine exposure will be summarized for the all-treated population. Duration of treatment, total number of cycles dosed, total dose received (in μg and $\mu\text{g}/\text{kg}$), average dose per cycle (in μg and $\mu\text{g}/\text{kg}$), and relative dose intensity (actual dose taken / planned dose) will be tabulated. Patients will receive 45 $\mu\text{g}/\text{kg}$ every 3 weeks (Q3W) for 2 cycles, then 30 $\mu\text{g}/\text{kg}$ Q3W for subsequent cycles as planned. When actual weight adjusted dose is needed, the last available weight before each infusion will be used. Patients with a BMI $\geq 35 \text{ kg/m}^2$ will have their dose calculated based on an adjusted body weight as follows:

$$\text{Adjusted body weight in kg} = 35 \text{ kg/m}^2 * (\text{height in meters})^2$$

Dose administered at each infusion (μg) is calculated by concentrated investigational product (IP) volume (in mL)* 5 mg/mL *1000. For incomplete infusion, adjust the calculated prepared dose by multiplying a factor of (1- volume of dosing solution not administered [in mL]/ [50 + total volume of reconstituted solution] mL) for lyophilized formulation. The number of patients who received camidanlumab tesirine at each cycle will also be tabulated using frequency counts and percentages.

Dose delays, interruptions, and reductions may also be analyzed if relevant. A cycle is delayed if it starts more than 2 days post- scheduled date.

Relative dose intensity will be additionally presented categorized (<60%, ≥ 60 - <80%, ≥ 80 - <90%, ≥ 90 - <110%, ≥ 110 %).

Exposure data and infusion details will be listed together.

4.7.2 Pre-medication and Prophylactic Medications for Hypersensitivity

Pre-medication and prophylactic medications for hypersensitivity will be listed only.

4.7.3 Subsequent Anticancer Therapy or Procedure

Patients' subsequent anticancer therapies or procedures including systemic therapy, conditioning/mobilization chemotherapy, CAR-T, transplant, or other (e.g. radiation), along with the start date of new anticancer therapy or procedure will be collected and listed only.

4.8 Safety Analyses

The summary of safety results will be presented.

General common rules

All safety analyses will be performed on the all-treated population, unless otherwise specified, using the following common rules:

- The baseline value is defined as the last non-missing value or measurement taken up to the first dose in the study.
- The analyses of the safety variables will be essentially descriptive and no systematic testing is planned.
- If relevant, selected safety analyses will be summarized by age, sex, racial subgroups, and any pertinent subgroups.
- The toxicity grade according to the Common Terminology Criteria for Adverse Events (CTCAE) version 4.0 will be taken into account in the summary. For patients with multiple occurrences of the same event, the maximum grade is used. If a patient has both missing and non-missing severity grades for treatment-emergent adverse events (TEAEs) within the same preferred term (PT), the patient will be counted under the non-missing severity grade.

4.8.1 Adverse Events, Serious Adverse Events, and Deaths

4.8.1.1 Analyses of adverse events

The primary focus of adverse event reporting will be on TEAEs. An adverse event (AE) will be considered to be a TEAE if it begins or worsens on or after the first dose date and until 30 days after the last dose date, or start of a new anticancer therapy/procedure, whichever comes earlier.

An AE occurring before the first dose or more than 30 days after the last dose date or after the start of a new anticancer therapy/procedure will not be included in TEAE displays, but will be listed as non-TEAEs.

If an AE date/time of onset (occurrence, worsening, or becoming serious) is incomplete, an imputation algorithm will be used to classify the AE as pre-treatment, TEAE, or post-treatment. The algorithm for imputing date/time of onset will be conservative and will classify an AE as treatment-emergent unless there is definitive information to determine it is a non-TEAE (pre- or post-treatment). Some details on classification of AEs with missing or partial onset dates are provided in Section 8.

Analysis of all TEAE(s):

The following TEAE summaries will be generated for the all-treatment population.

- Overview of TEAEs, summarizing number of TEAE and number (%) of patients with any
 - TEAE
 - Related TEAE (including possibly related, probably related, or related)
 - Any TEAE \geq Grade 3
 - Serious TEAE
 - TEAE leading to death
 - TEAE leading to permanent treatment withdrawal
 - TEAE leading to camidanlumab tesirine delay or reduction or interruption (if applicable)
 - TEAE with at least one infusion related reaction
 - TEAE of special interest
- All TEAEs \geq Grade 3 by PT, showing number (%) of patients with at least one TEAE, sorted by decreasing incidence of PTs
- All post-treatment/treatment-emergent AEs of special interest by PT, showing number (%) of patients with at least one TEAE of special interest, sorted by decreasing incidence of PTs
- All TEAEs by primary System Organ Class (SOC) and PT, showing number (%) of patients with at least one TEAE, sorted by SOC in alphabetic agreed order and decreasing incidence of PTs within SOC. This sorting order will be applied to all other tables, unless otherwise specified.
- All TEAEs by primary SOC, PT and Maximal CTCAE grade, showing number (%) of patients with at least one TEAE, sorted by SOC in alphabetic agreed order and decreasing incidence of PTs within SOC. This sorting order will be applied to all other tables, unless otherwise specified.
- All TEAEs \geq Grade 3 by primary SOC, PT and Maximal CTCAE grade
- All related TEAEs by primary SOC, PT and Maximal CTCAE grade (including possibly related, probably related, or related)
- All TEAEs leading to treatment withdrawal by primary SOC, PT and Maximal CTCAE grade
- All TEAEs leading to dose delay by primary SOC, PT and Maximal CTCAE grade

- All TEAEs leading to dose reduction by primary SOC, PT and Maximal CTCAE grade
- All TEAEs leading to infusion interruption by primary SOC, PT and Maximal CTCAE grade
- All TEAEs with fatal outcome by primary SOC, PT and Maximal CTCAE grade
- All Serious TEAEs by primary SOC, PT and Maximal CTCAE grade
- All infusion related reaction TEAEs by primary SOC, PT and Maximal CTCAE grade
- All post-treatment/treatment-emergent AEs of special interest by primary SOC, PT and Maximal CTCAE grade
- Summary of grouped post-treatment/treatment-emergent AEs selected by Standardised MedDRA Query (SMQ), ADCT modified SMQ, pre-specified SOC will also be provided by Grouped PT term, and Maximal CTCAE grade.
- Summary of TEAEs will also be provided by demographic factors including: sex, age group, race, disease subtype if appropriate.
- Time to onset of certain types of AEs will be summarized or presented using Kaplan-Meier plot if appropriate.

AE of special interest (AESI) is defined in the study protocol. Potential AESIs are identified per the pre-specified list of preferred or lower level terms based on customization of SMQs which satisfying the conditions as defined in protocol (level 1 adjudication). Final AESIs are identified through the review of individual potential AESIs by clinical team (level 2 adjudication).

All TEAEs, all serious adverse events (SAEs), all TEAEs leading to treatment withdrawal, all TEAEs leading to dose reduction, all TEAEs leading to dose delay, all TEAEs considered infusion related reactions, all TEAEs with fatal outcome and non-TEAEs will be listed.

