7.4.6 Pregnancy Test

A highly sensitive β -HCG test in urine or blood β -HCG test will be performed in WOCBP for eligibility (see Section 5.1) and throughout the study as per SoE (Table 1).

The C1D1 pre-dose pregnancy test can be waived if the test for eligibility was done within 7 days of C1D1. After starting the study drug, the interval between 2 consecutive pregnancy tests should be no more than 6 weeks.

The EOT pregnancy test should be performed \geq 9.5 months after the last dose of study drug (i.e., end of relevant systemic exposure considering 5 half-lives plus 6 months for other than aneugenic genotoxic compound). If the EOT visit is planned less than 9.5 months after the last dose of study drug, the patient will be asked either to come back to the site for a pregnancy test or she will be given a pregnancy kit to perform the test at home and the result collected over the phone. Both the phone contact and the result of the pregnancy test must be documented on source documents at the site.

If a pregnancy test is positive, the study drug must be held pending confirmation. If the pregnancy is confirmed, camidanlumab tesirine treatment will be discontinued permanently for the patient. Refer to Section 8.6 for the handling of the patient and reporting the event.

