All AEs, AESIs, and SAEs, regardless of relationship to study drug, will be reported from the time the patient signs the ICF until 30 days after the last dose of study drug; thereafter, only related SAEs will be reported [For German Sites Only: thereafter, only SAEs will be recorded (irrespective of the relationship to the study drug)]. The exception to this is patients who have responded to camidanlumab tesirine and undergo HSCT (either autologous or allogeneic) after permanent discontinuation of camidanlumab tesirine treatment without any intervening anticancer therapy to treat relapsing disease (mobilization/conditioning treatment for HSCT is allowed) or who have received CAR-T as the immediate subsequent anticancer therapy (mobilization/conditioning treatment for CAR-T is allowed). These patients will have the following safety information reported until 180 days post-HSCT/post-CAR-T regardless of relationship to camidanlumab tesirine:

- \geqrapsize Grade 3 AEs suggestive of hepatic toxicity, veno-occlusive disease/sinusoidal obstruction syndrome, graft-versus-host disease, infectious complications, potentially immune-mediated adverse events, prolonged cytopenia(s), and pulmonary toxicity
- In addition, for CAR-T therapy, any ≥ Grade 3 AEs of cytokine-release-syndrome and neurological toxicity

- SAEs
- Death

Whenever possible, AEs should be reported as a diagnosis rather than individual signs and symptoms. If no diagnosis is available or has been identified, then the primary symptom is reported.

In general, the term 'disease progression' should not be used for reporting an AE/SAE. However, AEs/SAEs that are complications of disease progression should be reported.

All AEs reported or observed during the study will be recorded on the AE page of the eCRF. Information to be collected will include event term, date of onset, assessment of severity (Section 8.3), seriousness (Section 8.1), relationship to study drug (Section 8.4), action taken with study drug, date of resolution of the event or ongoing (when no resolution by the end of the reporting period), any required treatment or evaluations, and outcome.

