4.8.1.3 AE for Transplant/CAR-T patients

The following analysis will be performed for patients who have responded to camidanlumab tesirine and undergo HSCT (either autologous or allogeneic) after permanent discontinuation

of camidanlumab tesirine treatment (without any intervening anticancer therapy to treat relapsing disease but mobilization/conditioning treatment for HSCT is allowed) or who have received CAR-T as the immediate subsequent anticancer therapy (mobilization/conditioning treatment for CAR-T is allowed) (i.e., patient in SCT population/CAR-T population) . The data will include the following information reported until 180 days post-HSCT/post-CAR-T regardless of relationship to camidanlumab tesirine.

- Summary of AEs \geq Grade 3 suggestive of hepatic toxicity, veno-occlusive disease/sinusoidal obstruction syndrome, graft-versus-host disease, infectious complications, potentially immune-mediated adverse events, prolonged cytopenia(s), and pulmonary toxicity
- In addition for CAR-T patients, summary of \geq Grade 3 AEs of cytokine-release-syndrome and neurological toxicity
- SAEs by primary SOC, PT and Maximal CTCAE grade
- Number (%) of patients who died after HSCT/CAR-T and reasons for death

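### Drug-related SAEs that start after the TEAE window are collected, but no all-treated SAE table and no table by relatedness includes them

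*SAP*

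**What the plan says.** SAP 4.8.1.1 counts an adverse event as treatment-emergent from the first dose "until 30 days after the last dose date, or start of a new anticancer therapy/procedure, whichever comes earlier". Events outside that window "will not be included in TEAE displays, but will be listed as non-TEAEs". The overview counts and the Grade 3 or higher and fatal-outcome tables are restricted to TEAEs. So are the table of "All related TEAEs by primary SOC, PT and Maximal CTCAE grade" and the table of "All Serious TEAEs by primary SOC, PT and Maximal CTCAE grade".

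Protocol 8.2 sets a different limit for collection. All AEs are reported "until 30 days after the last dose of study drug; thereafter, only related SAEs will be reported". No end date is given for those related SAEs. There are two exceptions:
- German sites record all SAEs after day 30, whatever the cause.
- Responders who go to HSCT, and patients whose immediate next therapy is CAR-T, have all SAEs, deaths and selected Grade 3 or higher events reported to 180 days after the procedure.

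Some SAP outputs do reach past the window:
- The AESI tables and the grouped SMQ/SOC table in 4.8.1.1 include post-treatment events.
- SAP 4.8.1.2 counts all deaths during the study.
- SAP 4.8.1.3 gives "SAEs by primary SOC, PT and Maximal CTCAE grade" for the SCT and CAR-T populations, to 180 days and without regard to causality.
- All SAEs are listed.

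**The concern.** Outside the two exceptions, an SAE that starts after day 30 enters the database only because it was judged related to study drug. These events bear directly on the toxicity profile, yet they are left out of both the related and the serious table. A related SAE within 30 days of the last dose is left out in the same way if a new therapy or procedure has already started.

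The half-life makes this more than a formality. Protocol 7.4.6 derives its 9.5-month interval from the "end of relevant systemic exposure considering 5 half-lives plus 6 months for other than aneugenic genotoxic compound". That places the end of relevant exposure well beyond day 30, so delayed drug-attributed events are plausible. The Summary of Changes for Amendment 5 says that the half-life had recently been revised, whereas the SAP was written against Amendment 1.

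At stake is the count of serious toxicity attributed to the drug. Adding the late events could raise that count or leave it unchanged, but could not lower it.

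**Working it through.** **1. Where a late related SAE would appear.** Take an SAE judged related, with onset after day 30 or after a new therapy or procedure.

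| Output | Reaches past the TEAE window? | Limit |
|---|---|---|
| Overview counts; related, serious, fatal-outcome and Grade 3+ tables (SAP 4.8.1.1) | No | TEAEs only |
| AESI tables (SAP 4.8.1.1) | Yes | AESIs only; Protocol 8.1.1 is mainly neurologic and immune-mediated and leaves out most rashes |
| Grouped SMQ/SOC table (SAP 4.8.1.1) | Yes | Groups not named; not split by relatedness or seriousness |
| Deaths (SAP 4.8.1.2) | Yes | Fatal events only, as deaths with reasons |
| SAEs after HSCT/CAR-T (SAP 4.8.1.3) | Yes, to 180 days | SCT and CAR-T populations only; any causality |
| SAE and non-TEAE listings | Yes | No counts |

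So no all-treated SAE table and no table by relatedness includes the event. Outside the AESI, grouped-term and SCT/CAR-T outputs it is only listed, and if fatal also counted as a death.

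**2. Kind of event affected.** Drug-related treatment-emergent SAEs in Phase 1 (Protocol 1.3) included pyrexia (6), dyspnea (4), pleural effusion (4), febrile neutropenia (2) and peripheral edema (2). Protocol 8.1.1 names none of these as an AESI. They show the type of event, not how many would occur late.

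**3. Drug remaining at day 30.** No half-life is stated, so the 9.5 months cannot be reproduced independently; it can only be solved backwards.

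- Five half-lives = 9.5 − 6 = 3.5 months.
- With a 30.44-day month: 3.5 × 30.44 = 106.5 days, and half-life = 106.5 / 5 = 21.3 days.
- Share remaining at day 30 = 2^(−30/21.3) = 0.377, about 38%.
- Exposure period left after day 30 = 106.5 − 30 = 76.5 days.

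Sensitivity to month length, and to 3.5 months having been rounded up from 3.0 (an assumption):

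| Days per month | Half-life, 3.5 months | Remaining at day 30 | Half-life, 3.0 months | Remaining at day 30 |
|---|---|---|---|---|
| 28 | 19.6 d | 34.6% | 16.8 d | 29.0% |
| 30 | 21.0 d | 37% | 18.0 d | 31.5% |
| 30.44 | 21.3 d | 37.7% | 18.3 d | 32.0% |
| 31 | 21.7 d | 38.4% | 18.6 d | 32.7% |

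Exactly one third remains when the half-life is 18.9 days, that is, when five half-lives are 3.11 months of 30.44 days. The fair statement is therefore roughly a third.

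**The case against.** The SAP follows the protocol. Protocol 9.8.1 uses the same TEAE window, including the cut at new therapy, and makes TEAEs the focus of AE summaries. The current amendment revised the half-life-based interval and kept that window. Full AE collection stops at day 30, so a rate that pools all time would mix complete with restricted ascertainment. All SAEs are listed, so nothing is hidden. The half-life is inferred from a contraception and pregnancy-test interval. The analyte is not named, the rounding is unknown and single-phase decay is assumed; an early distribution phase would lower the share remaining. The grouped table might also pick up effusion or infection, because its groups are not named.

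All of this stands. It makes the point a gap in tabulation, not a contradiction, and it is why the fix must keep the TEAE tables and show late events separately. It does not remove the gap, because a listing gives no count. By carrying AESIs past the window, the SAP itself accepts that day 30 is too early a stop for some purposes.

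A reader might infer three stronger points that the documents do not support:
- **That late related SAEs are missing from every related or serious table.** SAP 4.8.1.3 tabulates SAEs to 180 days after HSCT or CAR-T, and the AESI and grouped tables cover post-treatment events.
- **That the shortfall is greatest in patients who move quickly to transplant.** Responders going to HSCT without intervening therapy form the SCT population, which has extended collection and its own SAE table. They are among the best covered after the window closes.
- **That a related-SAE rate would shift by a known amount from the Phase 1 figure of 24/77 (31%).** The SAP plans separate related and serious TEAE counts and no rate for related SAEs. The documents give no count of late events, so any shifted percentage would rest on invented numbers.

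**Conclusion.** The gap is real but narrow. A related SAE after day 30, or after a new therapy or procedure, is collected but enters no all-treated SAE table and no table by relatedness. If it is not an AESI, not a grouped term and not in an SCT or CAR-T patient, it is only listed, or if fatal also counted as a death. The number of such events cannot be estimated from the documents.

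The pharmacokinetic support is that roughly a third of the drug may remain when the window closes. This rests on the 3.5 months derived from Protocol 7.4.6, on single-phase decay and on an unnamed analyte. The tabulation gap does not depend on it. This is a low-cost improvement to safety reporting; it does not affect the primary analysis.

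**What to change.** Keep the TEAE tables. Add one all-treated table to SAP 4.8.1.1: *SAEs related to camidanlumab tesirine with onset any time after first dose*, by SOC, PT and maximum grade. Give columns for onset within the TEAE window, after day 30, and after a new anticancer therapy or procedure. State how an event that meets both of the last two descriptions is assigned, and count each patient once in any total.

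Limit the table to related SAEs so that all-SAE recording at German sites does not distort it. Add a footnote that after day 30 only related SAEs are collected, apart from the German-site and HSCT/CAR-T exceptions, so ascertainment is less complete there than inside the window.

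The cost is one table from data already in the database. The count of related SAEs may look slightly less favourable, and the late columns need the stated caution in reading. No clinical rule or collection procedure changes.
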